Inclusion criteria: (1) aged 18 years or above; (2) patients with one or more peripheral lung nodules suspected to be lung cancer or poorly absorbing lesions on conventional anti-infective therapy; (3) patients with nodule diameters \leq 30 mm (diameters mentioned in the text are the average of the maximum and minimum diameters; (4) the nodules were pure ground glass nodules, partially solid nodules, or solid nodules; (5) the nodule is surrounded by lung parenchyma and is not visible in the bronchial lumen above the segment.

Exclusion criteria: (1) preoperative judgment that it is difficult for the patient to benefit from bronchoscopic biopsy (e.g., high risk of bleeding due to perivascular encasement of the lesion, difficulty in reaching the airway adjacent to the lesion due to previous lung surgery, etc.); (2) those with incomplete clinical data; (3) those with missing visits after biopsy.

Interventions

After stratification according to the size of the lesion and the proportion of solid components in the lesion (\geq 50%, <50%), the eligible subjects were randomized into the new navigation system group (experimental group) and the old navigation system group (control group) in a 1:1 ratio. All included subjects underwent transnavigation-guided bronchoscopic lung biopsy at the respiratory endoscopy center. For pre-biopsy navigation path planning, the small airway reconstruction system-pro (SARS-pro) (self-developed by our team) was used in the experimental group and the conventional VBN system (LungPro; Bronchus Corporation) in the control group. The SARS-pro navigation system is an augmented reality optical navigation system based on VBN, which upgrades the small airway tree reconstruction navigation system through deep learning and multiple trainings.

Outcomes

The primary outcome was the diagnostic positive yield of the different navigation systems for PPL. The second outcome was the adverse events (hemoptysis, pneumothorax, and mediastinal emphysema) of the subjects.

Ethical approval and informed consent statement

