The trial was approved by the Ethics Committee of the Sir Run Run Shaw Hospital, Zhejiang University School of Medicine (approval number: 2024-1000) (See the attachment "Ethics Approval Document"). For statistical analysis, subject identities were expressed as codes, which did not involve disclosure of subjects' privacy and personal information, and the study did not involve commercial interests, so informed consent was waived by the Ethics Committee (See the attachment "Informed consent form").

Statistical analysis plan

Official Title of the study: Research on New Intelligent Diagnosis and Treatment Technologies for Early Lung Cancer Based on Multimodal Imaging Bronchoscopy Navigation

Date of the document: May 20, 2024

Research on New Intelligent Diagnosis and Treatment Technologies for Early Lung Cancer Based on Multimodal Imaging Bronchoscopy Navigation

Statistical analysis

For sample size calculation, a study reported a deep learning-based airway segmentation algorithm based on 40 CT images. Based on the benefit of a larger sample size in deep learning, the sample size in this study was set to 100. For subject characteristics, the quantitative data were tested for normality using the skewness and kurtosis methods, and the homogeneity of variance was tested using the Levene test. Normal distribution measurement data were described as mean and standard deviation [Mean (±SD)], and t test or t' test was utilized for comparison between groups. Nonnormal data were summarized as median and interquartile range [M (Q_1 , Q_3)], and group comparisons were made using the Wilcoxon rank sum test. Count data were reported as the number of cases and composition ratio [n (%)], and the chi-square test or the Fisher exact test was utilized for comparison between groups. Data cleaning was accomplished using Python 3.9.12 (Python Software Foundation, Delaware, USA), and the difference comparison was completed by R version 4.3.3 (R Foundation for Statistical Computing, Vienna, Austria). Statistical significance was set to P<0.05.

Data management and confidentiality

(1) The data is stored in the hospital's server with strict security protection and is not accessible to external networks; (2) All information related to the identity of the CT's patients is kept confidential, and the relevant information is not disclosed to the public outside of the scope permitted by relevant laws and/or regulations.

Ethics Committee Approval (Original Chinese version)

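### The SAP ties no analysis to diagnostic yield; its count-data rule gives no difference with CI, leaves the correction open and ignores the randomisation strata, which costs power and information but not validity

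*Combined protocol and SAP*

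**What the plan says.** The protocol's Outcomes section states: "The primary outcome was the diagnostic positive yield of the different navigation systems for PPL". Under Interventions, patients are allocated 1:1 "After stratification according to the size of the lesion and the proportion of solid components in the lesion". Solid component is split at 50%; no cut-points are given for size.

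The SAP's Statistical analysis section is one paragraph. Its methods begin "For subject characteristics, the quantitative data were tested for normality". For binary data it says "Count data were reported as the number of cases and composition ratio", and then that "the chi-square test or the Fisher exact test was utilized for comparison between groups". It adds that "the difference comparison was completed by R version 4.3.3" and sets significance at P<0.05, without saying whether tests are two-sided. Yield is not named. On size it says that "the sample size in this study was set to 100", without saying whether that means patients in total, patients per arm or CT images.

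**The concern.** The count-data sentence follows an opening about subject characteristics, so it may describe only the baseline table. On the kinder reading it also covers yield, and three gaps remain:

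1. Two tests are named with no rule for choosing between them and nothing on continuity correction. Naming the software does not say which option is set.
2. Only counts and percentages by arm are planned. A p-value alone shows neither how large the gain in yield is nor how uncertain.
3. Randomisation is stratified and the test is not. This gap is minor and conditional: it matters only if the strata predict yield.

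At stake are the power of the primary comparison, how informative its result is, and whether the choice of test is settled before outcomes are compared by arm.

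**Working it through.** **Inputs.** From the documents: 1:1 allocation, a sample size of 100, alpha 0.05, and an 80% yield for navigation bronchoscopy overall (protocol, Background), used here as the control yield. Assumed: 100 analysed patients in total, two-sided tests, experimental yields of 90% and 94%, and, for stratified results, four equal strata with blocks of 4. The 100 cannot be reproduced as a comparison of yields, because no effect size or power is given.

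**One table.** Take 40/50 vs 47/50. The smallest expected count is 50 × 13/100 = 6.5, so a conventional expected-count rule would select chi-square.

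- Uncorrected: N(ad − bc)²/(r1·r2·c1·c2) = 100 × (40×3 − 10×47)²/(50×50×87×13) = 100 × 350²/2,827,500 = 4.33, p = 0.037.
- Corrected: 100 × (350 − 50)²/2,827,500 = 3.18, p = 0.074.
- Fisher: p = 0.071.

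At 39/49 vs 48/51 (smallest expected count 6.4) the three p-values are 0.031, 0.063 and 0.039.

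**All tables, exact enumeration.** Share of trials in which uncorrected and corrected chi-square disagree at 0.05:

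| Control/experimental | 80% vs 90% | 80% vs 94% |
|---|---|---|
| 50/50 | 10.8% | 15.5% |
| 49/51 | 7.8% | 11.5% |
| 51/49 | 10.6% | 14.0% |
| 48/52 | 10.5% | 14.2% |
| 52/48 | 9.0% | 11.4% |

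Averaged over the arm sizes that blocks of 4 produce, this is about 10% and 14%. Excluding "those with missing visits after biopsy" makes an exact 50/50 split less likely, so the other rows matter. If 100 means per arm, the figures are 9.3% and 6.7%.

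**Power** at 50/50, 80% vs 94%: 0.584 uncorrected; 0.429 corrected or Fisher.

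**False positives** at a common 80% yield, 50/50: 5.2% uncorrected, 2.8% corrected, 2.8% Fisher. The chance that any of the three is below 0.05 is also 5.2% (5.1% at 49/51 and 48/52), because every table significant by the other two was significant by uncorrected chi-square.

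**Effect.** For 40/50 vs 47/50 the difference is 0.94 − 0.80 = 14.0 points. Wilson limits are 0.670 to 0.888 (control) and 0.838 to 0.979 (experimental). The Newcombe limits are 0.14 − √[(0.94 − 0.838)² + (0.888 − 0.80)²] = 0.005 and 0.14 + √[(0.979 − 0.94)² + (0.80 − 0.670)²] = 0.276, that is 0.5 to 27.6 points.

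**Stratification.** Simulation, unstratified uncorrected chi-square against CMH, overall about 80% vs 94%:

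| Control yields by stratum (%) | Type I error, chi-square / CMH | Power, chi-square / CMH |
|---|---|---|
| 80, 80, 80, 80 (flat) | 5.1% / 4.9% | 0.574 / 0.566 |
| 70, 80, 80, 90 (mild) | 4.8% / 5.0% | 0.574 / 0.575 |
| 65, 75, 85, 95 (moderate) | 4.3% / 4.9% | 0.575 / 0.588 |
| 50, 76, 96, 98 (strong) | 2.7% / 5.0% | 0.577 / 0.637 |

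The change in power from stratifying is −0.8, +0.1, +1.3 and +6.0 points. With exactly 50 per arm it is −2.0, −1.2, 0.0 and +4.7.

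**The case against.** The strongest reply is that nothing here produces false claims. That stands. A reader might infer that an open choice of test lets the team pick its way to significance at an inflated error rate. Among the three tests the text allows, it does not: the best of the three rejects no more often than uncorrected chi-square alone, about 5%. The disagreement rates arise under a true benefit and measure lost power. Nor is the unstratified test invalid; it is conservative if the strata predict yield.

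A reader might also infer that the primary outcome has no analysis at all. The text is too ambiguous for that, since the count-data sentence can be read as general.

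An expected-count rule would shrink the problem, not remove it. With Fisher used below 5 and chi-square otherwise, the open correction still changes the verdict in 9.3% (80% vs 90%) and 11.5% (80% vs 94%) of trials.

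It is fair to say that stratifying gains little unless the gradient is strong. The Background suggests that yield is lower for lesions under 1 cm but gives no rates by size, and nothing is said on solid component. An unstratified named test with a difference and CI would close the first two gaps. Stratifying is still preferable, because it follows the design, holds its level across gradients and costs almost nothing.

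**Conclusion.** The concern holds as a loss of power and information, with an avoidable discretionary choice, and should be corrected. The textual gaps need no assumption: yield is not linked to an analysis, no difference with CI is planned, the correction is unstated and the strata are unused.

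The sizes are conditional. With about 50 per arm and 80% vs 90-94%, the correction alone changes the verdict in roughly 8-15% of trials, and at 50/50 it moves power between 0.58 and 0.43 (80% vs 94%). If the strata predict yield, the unstratified test runs at about 2.7-4.8% instead of 5%. All of this rests on assumed yields, strata, block size, two-sidedness and analysed number, because the documents do not say what the 100 counts.

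**What to change.** Before outcomes are compared by arm, state in the SAP:

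- **Primary analysis:** the Mantel-Haenszel risk difference in yield (experimental minus control) with 95% CI, stratified by the strata actually used at randomisation, with size cut-points taken from the randomisation records.
- **Test:** CMH without continuity correction, two-sided 0.05. The CMH p-value decides; in simulation the CI and the test disagreed in 5-6% of trials.
- **Unit:** one result per patient, or a method that allows for several lesions per patient, since the inclusion criteria admit more than one nodule.
- **Pooling:** pool over size if any stratum has fewer than 5 patients in either arm. This rule uses patient counts, not outcomes.
- **Sensitivity analyses:** the unstratified difference with Newcombe CI, and one unstratified test named in advance.

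The cost is SAP wording, retrieval of the cut-points and a few lines of R, with no new patient data. Power falls by up to about 2 points if the strata do not predict yield; the gain is about 0-1 point for mild to moderate gradients and about 6 only for a strong one. Pooling over size costs 0 to about 2 points against full stratification.

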Study protocol

Official Title of the study: Research on New Intelligent Diagnosis and Treatment Technologies for Early Lung Cancer Based on Multimodal Imaging Bronchoscopy Navigation

Affiliation: Sir Run Run Shaw Hospital, Zhejiang University School of MedicineDepartment: Department of Respiratory and Critical Care MedicineDate of the document: May 20, 2024

Research on new intelligent diagnosis and treatment technologies for early lung cancer based on multimodal imaging bronchoscopy navigation

Background

Lung cancer is one of the malignant tumors with the highest incidence and mortality rates worldwide. From the 1970s to the present, the mortality rate of lung cancer in China has been climbing year by year, and currently lung cancer ranks first in China in terms of incidence rate and mortality rate. Meanwhile, data show that 75% of lung cancer patients are already in advanced stage when they are diagnosed. The 5-year survival rate of advanced lung cancer in China is only 16.1%, while the 5-year survival rate of early lung cancer patients can reach 73%. Therefore, improving the early diagnosis rate of lung cancer will greatly reduce the mortality rate of lung cancer.

Regular chest computed tomography (CT) in the population can detect a large number of nodular lung lesions, and data show that lung nodules are detected in approximately 25% of the population on routine screening, most of which (96.4%) are benign. Further examination of these high-risk lung nodules is effective in improving early lung cancer detection and reducing mortality by approximately 20%. CT-guided percutaneous lung puncture is the mainstay of conventional diagnosis of lung nodules, and the risk of complications is a major concern. Its complications include pneumothorax, hemoptysis, and needle tract metastasis, among which the incidence of pneumothorax is 12.3% and hemoptysis is 20%. In recent years, the use of navigational tracheoscopy for peripheral lung nodule biopsy has gradually increased in the clinic due to good safety and accuracy. 2020 CHEST published a meta-analysis on navigational tracheoscopy, the incidence of pneumothorax is only 2%, which is obviously advantageous compared with the traditional methods.

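### Adverse events would be compared by P value alone; with about 50 patients per arm, a non-significant result is weak evidence on safety

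*Combined protocol and SAP*

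**What the plan says.** The protocol's Outcomes section names one secondary outcome: "The second outcome was the adverse events (hemoptysis, pneumothorax, and mediastinal emphysema) of the subjects". It gives no margin, grading, time window or pooled endpoint.

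The SAP's Statistical analysis section does not mention adverse events. Its rule for count data is a summary by number and percentage, followed by a test: "the chi-square test or the Fisher exact test was utilized for comparison between groups". The threshold is given as "Statistical significance was set to P<0.05". The SAP does not say how to choose between the two tests, whether chi-square is continuity-corrected, whether tests are two-sided, or how a non-significant result is to be read. It plans no risk difference, ratio or confidence interval. The rule stands in a run of text introduced as concerning subject characteristics, so it is not expressly assigned to adverse events. No other rule could cover them.

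On size, the SAP says "the sample size in this study was set to 100", reasoning from the fact that "a study reported a deep learning-based airway segmentation algorithm based on 40 CT images". No event rate or power enters that choice. Allocation is 1:1 (protocol, Interventions).

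The protocol's Background supplies two pneumothorax rates. For navigational bronchoscopy, "the incidence of pneumothorax is only 2" percent. For CT-guided percutaneous puncture, "the incidence of pneumothorax is 12.3% and hemoptysis is 20" percent.

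**The concern.** At 2%, one pneumothorax is expected in an arm of 50. With so few events a test at 0.05 has little power, and its P value alone cannot separate an absence of excess from a substantial excess. An interval can, because it shows which differences the data leave open.

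This matters here because the Background presents the low pneumothorax rate as an advantage of navigational bronchoscopy. The experimental software was developed by the study team to open up airways below 3 mm, and near-pleural lesions are named as the difficult ones. A reader will want to know how large an excess of complications the trial can exclude. The planned analysis does not supply that answer.

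**Working it through.** **No figure to reproduce.** The SAP states no power, and 100 cannot be derived from the 40-image comparison.

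**Inputs**
- n = 50 per arm: 100 read as the trial total, split 1:1.
- Alpha = 0.05 from the SAP; two-sided is assumed.
- Pneumothorax 2% (control) and 12.3% (raised rate), both from the Background. The second is used only as a familiar yardstick.

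**Expected events.** 50 × 0.02 = 1 and 50 × 0.123 = 6.15. The average is (1 + 6.15)/2 ≈ 3.6 per arm. This is below 5, where Fisher is the customary choice.

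**Power.** Sum Bin(i; 50, 0.02) × Bin(j; 50, 0.123) over all tables (i, j) with P<0.05.

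| Test | Power, 2% vs 12.3% |
|---|---|
| Fisher exact | 33.2% |
| Chi-square, Yates-corrected | 33.2% |
| Fisher if an expected count <5, otherwise uncorrected chi-square | 37.0% |
| Chi-square, uncorrected | 53.1% |

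For 2% vs 10%, power is 19.0% with Fisher and 38.3% with uncorrected chi-square.

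**What reaches significance.** Fisher needs 6/50 vs 0/50 (P=0.027) or 8/50 vs 1/50 (P=0.031). Uncorrected chi-square needs 4/50 vs 0/50 or 7/50 vs 1/50. The table closest to expectation, 6/50 vs 1/50, just misses under every version: Fisher P=0.112, Yates P=0.117, uncorrected P=0.05004.

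**What an interval adds.** Take 5/50 vs 1/50, a difference d = 0.10 - 0.02 = 0.08.
- Fisher P=0.20.
- Wilson 95% limits: 0.0435 to 0.2136 for 5/50, and 0.0035 to 0.1050 for 1/50.
- Newcombe lower limit: 0.08 - √[(0.10 - 0.0435)² + (0.1050 - 0.02)²] = 0.08 - 0.102 = -0.022.
- Newcombe upper limit: 0.08 + √[(0.2136 - 0.10)² + (0.02 - 0.0035)²] = 0.08 + 0.115 = 0.195.

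The interval is -2.2 to +19.5 points. For 1/50 vs 1/50 it is -8.7 to +8.7 points. Both tables are simply non-significant by P value, yet they support quite different statements about safety.

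**Sensitivity (Fisher, 2% vs 12.3% unless stated).**
- 45 per arm (10% loss): 27.9%.
- 40 per arm (20% loss): 21.2%.
- Control rate 1%, 3% or 4%, against 12.3%: 44.6%, 24.5%, 17.9%.
- If 100 meant per arm: 78.3% (85.4% with uncorrected chi-square).

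The loss rates are assumptions. Loss is relevant because patients with missing visits after biopsy are excluded.

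**The case against.** Several stronger readings are tempting, and the documents do not support them.

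- *A non-significant result tells us nothing about safety.* This is too strong. The 1/50 vs 1/50 interval excludes a 10.3-point excess (12.3 - 2). If both arms truly run at 2%, the Newcombe upper limit falls below 10.3 points about 65% of the time. A very large rise would also usually be seen: Fisher power is about 78% at 20%.
- *A rise to 12.3% would usually be missed.* This depends on the test. It holds for Fisher, for Yates and for the customary switching rule (missed 63% to 67% of the time). Under uncorrected chi-square, which the SAP does not exclude, it is close to a coin toss (missed 47%).
- *The trial will report that complications do not differ.* This is inference. The SAP sets a threshold and makes no claim of equivalence or equal safety.
- *All three adverse events are rare.* A low rate for navigational bronchoscopy is documented only for pneumothorax. The 20% hemoptysis figure belongs to percutaneous puncture, and no rate is given for mediastinal emphysema.
- *10.3 points is a safety margin.* It is a background contrast between two procedures. Both arms here have bronchoscopic biopsy and differ in planning software.

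It is also fair to say that counts and percentages will be shown, so a reader could compute an interval, and that the missing estimate affects the primary outcome too. Neither removes the point: the SAP should state what the safety conclusion will rest on.

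**Conclusion.** The point holds as a modest, inexpensive improvement. The only rule available for adverse events gives a P value with no estimate or interval. At 50 per arm, power for a pneumothorax rise from 2% to 12.3% is 33% with the test that fits these counts, and 33% to 53% across the tests the SAP allows. A P value above 0.05 is therefore weak evidence on safety, though not empty of information.

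The conclusion rests on reading 100 as the total, on two-sided testing, and on the Background's 2% applying to the control arm. At 100 per arm the low-power argument would largely fall away, but the case for reporting an interval would remain. If the count-data rule was not meant to cover adverse events, the SAP specifies no safety comparison at all, which is a larger gap with the same remedy.

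**What to change.** Add a short safety paragraph to the SAP:

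1. For hemoptysis, pneumothorax, mediastinal emphysema and any of the three, report counts and percentages by arm and the risk difference with a 95% confidence interval (Newcombe or Miettinen-Nurminen, one chosen in advance). A P value may stand beside it or be dropped.
2. Base the safety statement on the interval, and state that P>0.05 will not be described as similar safety.

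The 10.3-point difference between the two background rates may be mentioned as context when discussing the pneumothorax interval. It should not be made a mandatory reporting margin.

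The cost is a paragraph of SAP text and a few lines of R, with no extra patients or data. The downside is a safety statement that may look less favourable, since the intervals will be wide.
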